8.2.2 Intra-Examiner Reproducibility

All Examiners from the investigational sites will go through a training and calibration exercise before they may participate in the study. This will involve first a classroom discussion of the clinical criteria and scales that will be used followed by demonstration and measurement using volunteer patients. A "gold standard" periodontist or hygienist will first make clinical measurements on the patients, followed by each examiner. These measurements will then be repeated. Inter- and intra-examiner correlations will then be calculated. This process will be repeated until each examiner is correlated to the gold standard examiner.

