5.2.2 Primary Effectiveness Endpoint

The primary effectiveness endpoint is a composite endpoint that considers radiographic and clinical measurements at six months post-implantation: the amount of linear bone growth (LBG), which is assessed with the use of radiographs, and the regain from baseline of clinical attachment level (Δ CAL), which is assessed clinically. LBG is a representative measurement of alveolar bone re-growth that is measured in a vertical and horizontal direction using radiographs. The clinical attachment level (CAL) is the distance from the cemento-enamel junction (CEJ) (or other fixed

reference point) generally along the long axis of the tooth to the deepest extent of the periodontal pocket. CAL is the established clinical parameter to be used for evaluation of connective tissue regeneration and 1.5 mm is the historically established level of clinical efficacy for guided tissue regeneration (GTR) products that attempt to regenerate periodontal structures. The success criteria are a minimum of 1.5 mm for Δ CAL and a minimum of 1 mm for LBG. Both the Δ CAL and LBG must meet the success criteria for a subject to be considered a success.

LBG was selected as a component of the primary endpoint because it was shown to be the most sensitive measurement of alveolar bone re-growth in a recent trial for a different bone graft substitution used in a similar indication⁽⁶⁾. The soft tissue and bone components are each important to a clinically successful outcome and periodontitis, which by definition affects both the connective tissue like periodontal ligament and alveolar bone, is an established fact. Furthermore, in Sunstar dog studies, it was also demonstrated that β -TCP itself achieved a good bone regeneration but not cementum. Rh-bFGF must contribute to not only bone regeneration but also new cementum and matured periodontal ligament regenerations. Therefore, to determine whether this product achieves the regeneration of all periodontal tissues, the composite endpoint combining clinical parameter (Δ CAL) with radiographic parameter (LBG) was selected as the primary endpoint.

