8.0 STUDY PLAN

8.1 Study Procedures

The following sections describe the study procedures and data to be collected. Subjects will be assessed at the screening (Visit 1) and baseline (Visit 4) visits to determine and confirm eligibility. The identified target teeth at the screening visit (Visit 1) will be reconfirmed intra-operatively at the surgery visit (Visit 5), and one eligible tooth will be selected to receive the study treatment. Within 2 months prior to the study treatment, each subject will undergo thorough scaling and planing of all teeth in the target tooth's quadrant to control the disease process and minimize lesion variability (Visit 2 and if necessary, Visit 3). Note that a patient may have already undergone scaling and planing prior to screening. After study treatment, each subject will be monitored at periodic intervals to assess safety and effectiveness for at least six months. The Schedule of Study Procedures is located in Appendix A.

The Investigator and all study personnel will be blinded to the treatment. Only calibrated Examiners who are different from the surgeon performing the implantation should carry out the clinical evaluations to assess the study safety and effectiveness parameters. See Section 8.2 for calibration details.

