8.1.2 Clinical Outcomes

The Investigator and other qualified site personnel (i.e. Dentist, Dental Hygienist) will perform the clinical examinations using the following methods at the examination visits. Clinical Measurement will be performed throughout pre-treatment, baseline and post-treatment follow-up visits during the trial. Intra-Surgical Measurement will be performed at Visit 5 only.

Only calibrated North Carolina 15 mm periodontal probes will be used. The measurements will be rounded off to the nearest millimeter (0.5 mm is to be rounded up). Clinical probing measurements will be made at the mid-facial, mesial and distal line angles and at mid-lingual, mesial, distal line angles with a calibrated probe. The measurements will be made at these standard locations to the deepest part of the defect.

Clinical Measurement

- Pocket depth (PD): From free gingival margin to the base of the pocket
- Clinical attachment level (CAL): will be calculated by adding PD and GR.
- Gingival recession (GR): From the free gingival margin to the CEJ

Intra-Surgical Measurement (Visit 5 only)

- Alveolar crest height (ACH): From cemento-enamel junction to alveolar crest (CEJ-AC)
- Base of defect from CEJ (BD): From cemento-enamel junction to the base of osseous defect (CEJ-BD)
- Vertical bone defect depth at its deepest location (vBD): vBD will be calculated by subtracting ACH from BD

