8.2 Examiner Calibration

8.2.1 Training of Surgeons, and Training of Examiners

One to two periodontists from each investigational site will be trained to perform the surgeries. One individual will be designated as the primary surgeon and should perform most of the procedures. The other individual will be the back-up and may also perform any non-examiner procedures when the primary clinician is not available. All surgeons must have ample experience in periodontal regenerative procedures and receive training. Surgeons will be trained on the surgical technique, end point of root debridement, handling and placement of test materials and suturing technique. To insure standardization of the surgical procedures, training will be conducted to thoroughly review all aspects of the pre-surgical, surgical and post-surgical phases of the trial. This training will be carried out prior to the beginning of the trial.

In addition, two examiners (dentists or hygienists) will be trained on baseline, interim and final evaluation measurements, exclusive of clinical photographs. The examiners should be different individuals from the surgeons. The same examiner, if possible, should perform all measurements on a particular subject, *i.e.* baseline, interim, and final evaluation measurements, exclusive of clinical photographs.

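### Examiners are released on correlation with a gold standard, which in its usual forms ignores a constant offset, and a subject's examiner may change between baseline and 6 months

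*Protocol*

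**What the plan says.** Section 8.2.2 has a gold-standard clinician and then each examiner measure volunteer patients, and the measurements are repeated. The statistic is then given: "Inter- and intra-examiner correlations will then be calculated". The release rule follows: "This process will be repeated until each examiner is correlated to the gold standard examiner". No coefficient, cut-off, mean difference or limit of agreement is named.

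Section 8.2.1 provides more than one person to take the readings: "two examiners (dentists or hygienists) will be trained on baseline, interim and final evaluation measurements". Keeping one examiner per subject is preferred but not required: "The same examiner, if possible, should perform all measurements on a particular subject".

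The readings feed the primary endpoint. Section 8.1.2 says that CAL "will be calculated by adding PD and GR", and on resolution: "The measurements will be rounded off to the nearest millimeter (0.5 mm is to be rounded up". Section 5.2.2 dichotomises the result: "The success criteria are a minimum of 1.5 mm for Δ CAL and a minimum of 1 mm for LBG". A subject must meet both conditions. On blinding, Section 8.1 states: "The Investigator and all study personnel will be blinded to the treatment".

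**The concern.** Correlation measures whether two people rank and space the same patients alike. It does not measure whether they read the same number of millimetres. An examiner who always probes 1 mm deeper than the gold standard can correlate with it as well as one with no offset.

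If that examiner reads both baseline and 6 months, the offset cancels in the change. If a colleague reads one of the two visits, the difference between the two examiners is added to the change or taken from it. At a given probing site the readings are whole millimetres, so a gain of at least 1.5 mm means an observed gain of 2 mm or more, and a 1 mm offset is a full step on that scale. What is at stake is whether individual subjects are correctly classified on the CAL half of the primary composite. Section 12.1.10 uses that composite for dose selection.

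**Working it through.** **The plan's own figures.** The protocol gives no figure for examiner agreement and no mean or SD for CAL gain. Its only power figure (Section 12.1.2) is for LBG: 20 per group, difference 1.70 mm, SDs 1.20 and 2.30 mm, two-sided 5%. The standard error is √((1.20² + 2.30²)/20) = √0.3365 = 0.580, so the noncentrality is 1.70/0.580 = 2.93. With Welch df 28.6 the power is 0.81, which reproduces the stated 80% or more. LBG is read centrally from radiographs, so this point does not touch it.

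**Step 1: does correlation see an offset?** For a constant c, corr(g, e + c) = corr(g, e). To check that this survives rounding, paired readings were simulated (200,000 pairs; assumed true CAL mean 8 mm, SD 2.5 mm; reading error SD 0.5 mm; rounded to whole mm) with a constant offset added to the examiner.

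| Offset (mm) | Pearson | Spearman | Consistency ICC | Absolute-agreement ICC | Within 1 mm |
|---|---|---|---|---|---|
| 0 | 0.949 | 0.945 | 0.949 | 0.949 | 95% |
| 0.5 | 0.949 | 0.945 | 0.949 | 0.932 | 90% |
| 1 | 0.949 | 0.945 | 0.949 | 0.882 | 74% |
| 1.5 | 0.949 | 0.944 | 0.949 | 0.810 | 50% |
| 2 | 0.949 | 0.944 | 0.949 | 0.728 | 26% |

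The three ordinary coefficients do not move. The absolute-agreement ICC does, but at 1 mm it is still 0.882.

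**Step 2: effect in a subject whose examiner changes.** Let d be the amount by which the 6-month examiner reads deeper than the baseline examiner. The observed gain is the true gain minus d, so P(observed gain ≥ 1.5) = 1 − Φ((1.5 − (μ − d))/σ). With assumed μ = 2.0 mm and σ = 1.5 mm:

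| d (mm) | (1.5 − (2.0 − d))/1.5 | P(CAL criterion met) |
|---|---|---|
| −1 | −1.00 | 84% |
| −0.5 | −0.67 | 75% |
| 0 | −0.33 | 63% |
| 0.5 | 0.00 | 50% |
| 1 | 0.33 | 37% |

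A simulation with CAL rounded to whole millimetres gives the same five percentages. Over assumed mean gains of 1.5 to 3 mm and SDs of 1 to 2 mm, a 1 mm offset lowers the share by about 17 to 38 points or raises it by about 6 to 34. A 0.5 mm offset moves it by about 4 to 19 points.

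**Step 3: effect on an arm.** The shift in an arm's CAL rate is the share of subjects switched times the shift in Step 2. The share is not in the protocol. At an assumed 10%, a 1 mm offset always in the same direction gives 0.10 × (63 − 37) = 2.6 points down, or 0.10 × (84 − 63) = 2.1 points up. If switches run equally both ways, the switched subjects average (37 + 84)/2 = 60.5%, and the arm moves by 0.10 × (63 − 60.5) = 0.25 points. In an arm of 20, a 10% share is 2 subjects. With a one-directional offset of 1 mm deeper, about 2 × 0.26 = 0.5 subjects would be misclassified on CAL.

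**Step 4: effect on the composite.** Success also needs LBG of at least 1 mm, which the offset does not alter. For a given offset, the shift in the composite therefore cannot exceed the shift in the CAL component.

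**The case against.** The strongest reply is that the protocol does not specify a faulty coefficient, because it specifies none. A reader might infer that no correlation could detect an offset. The text does not support that, since an absolute-agreement ICC would react. What stands is narrower: the rule does not require such a measure, sets no cut-off for it, and is met by the ordinary coefficients that miss an offset.

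Second, the exercise is more than a coefficient. It includes discussion of criteria, demonstration, repeated readings on the same patients and further rounds if needed. These make a large offset less likely, but none of them is the release criterion.

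Third, the default is one examiner throughout, and an offset then cancels. This is correct and limits the harm to switched subjects.

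Fourth, a reader might infer that the treatment comparison is biased. The documents do not support that either. Study personnel are blinded, examiners are not the surgeons, and allocation is balanced within sites, so an offset should not depend on arm. Switches could fall unevenly by chance, but no bias is expected. The protocol also presents the trial as a feasibility study in which testing of the primary endpoint is not expected to be conclusive.

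It might also be said that such detail belongs in the analysis plan. However, release takes place before examiners take part, so an analysis plan cannot repair it. Section 8.1 also refers to Section 8.2 for the calibration details.

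**Conclusion.** The point holds as a minor but real weakness. Section 8.2.2 can be satisfied by two examiners who differ by a whole probing step, and Section 8.2.1 allows both to measure one subject. For a switched subject, a 1 mm offset takes the chance of meeting the CAL criterion from 63% to 37% or 84%. These figures rest on an assumed mean gain of 2.0 mm and SD of 1.5 mm, and they are not shifts in the composite or in the whole arm. How far an arm moves depends on how many subjects are switched and in which direction. At a 10% share it is roughly 0.25 to 2.6 points on CAL. The consequence is misclassification and lost precision in small arms. An offset could also shift the pocket-depth entry criterion of 7 mm if a calibrated examiner takes that reading, even without a switch.

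**What to change.** In Section 8.2.2, replace correlation as the release criterion with agreement, computed on the calibration readings already planned:

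- **Main criterion:** a pre-set limit on the mean signed difference from the gold standard, tighter than 1 mm (for example, within 0.5 mm). Two examiners at opposite ends of a 0.5 mm limit still differ by 1 mm, so the same limit is best applied to the difference between examiners at one site as well.
- **Support:** an absolute-agreement ICC and the percentage of exact agreement, each with a fixed pass mark.
- **Not sufficient alone:** the percentage within 1 mm. An examiner who reads exactly 1 mm deep every time scores 100% on it.

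In addition, record which examiner measured each subject at each visit, and repeat the primary analysis excluding subjects whose examiner changed between baseline and 6 months, as a sensitivity analysis.

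The cost is small: different statistics on the same data and one recorded item per visit. The downside is that some examiners may need a further calibration round.

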8.2.3 Radiographic Quality Assurance and Calibration

The independent radiographic center will conduct quality assurance and calibration procedures according to their procedures.

8.3 Schedule of Observations and Procedures

The schedule for all study-related procedures for all evaluations is shown in Appendix A. Assessments should be completed at the designated visit/time point(s).

8.3.1 Visit 1: Screening

After the Informed Consent for Screening is signed and a screening number is assigned, the screening assessment will be performed. It includes an oral, medical (including a complete record of current medications) and demographic history, smoking history and identification of one or more target teeth and bone defect(s). Note that only one tooth per subject may receive treatment

with the investigational product. However, the final study eligibility of a tooth cannot be determined until the surgery is underway. Therefore, identification of additional target teeth increases the likelihood that the subject will not be excluded from the study during surgery.

A periapical radiograph may be taken as necessary to ensure that all target teeth meet the inclusion and exclusion criteria (see Sections 6.1 and 6.2). If the subject satisfies all inclusion and exclusion criteria, one or more target teeth that meet the eligibility criteria will be identified. To be included in the study, a subject must undergo thorough scaling and planing of all teeth in the target tooth's quadrant within 2 months prior to the surgical procedure. If more than one target tooth is selected in more than one quadrant, each quadrant with a target tooth will undergo scaling and planing. Note that scaling and planing will be performed in other quadrants as necessary to treat disease. If scaling and planing are necessary, it should be performed at least two weeks prior to the Baseline Visit (Visit 4). If tissue inflammation caused by the pre-surgical treatment is observed at the Baseline Visit (Visit 4), the Baseline Visit should be postponed until the inflammation subsides.

A summary of all procedures to be performed is listed below.

Summary of Procedures/Measurements:

- Informed consent for screening must be obtained according to the process described in Section 14.2
- Complete Screening Assessment (CRF 1) and Pre-enrollment Eligibility and Assignment (CRF 2) forms
- Identify a single or, if possible, multiple target teeth
- Determine initial subject eligibility
 - If not eligible, subject is a screen failure and should be documented on the Screening Failure Log
 - If eligible, continue the visit
- Determine if 1 or 2 scaling and planing procedures and/or sustained oral hygiene instructions are necessary
 - If yes, schedule the procedure(s)
 - If no, Visit 4 (Baseline) may be conducted at the end of this visit
- If necessary:
 - Perform supragingival prophylaxis
 - Provide oral hygiene instructions
 - Obtain a full set of radiographs or a panorex
 - Complete a full mouth periodontal chart

- Obtain a periapical (PA) radiograph of the target tooth or teeth

8.3.2 Visits 2 and 3: Pre-Treatment Procedures

All subjects must receive a thorough scaling and root planing of all teeth in the target tooth's quadrant within 2 months before the surgical procedure. If more than one target tooth is selected in more than one quadrant, each quadrant with a target tooth will undergo scaling and planing. Note that scaling and planing will be performed in other quadrants as necessary to treat disease. If scaling and planing are necessary, it should be performed at least two weeks prior to the Baseline Visit (Visit 4). If tissue inflammation caused by the pre-surgical treatment is observed at the Baseline Visit (Visit 4), the Baseline Visit should be postponed until the inflammation subsides. The subjects will be instructed in oral hygiene including tooth brushing, and interproximal oral hygiene devices, as needed. Subjects are expected to demonstrate good plaque control prior to the surgical intervention.

A summary of all procedures to be performed is listed below.

Summary of Procedures/Measurements:

- Perform thorough scaling and planing of all teeth using local anesthetic as necessary
- Provide oral hygiene instructions

8.3.3 Visit 4: Baseline Examination

Visits 1(Screening) and 4 (Baseline) may occur on the same day if pre-treatment procedures (Visits 2 and 3) are not necessary. Visit 4 (Baseline) may be performed after the final pre-treatment (Visit 2 or 3) has been completed if the final pre-treatment visit occurs within 2 weeks before surgical treatment. If the window between Visit 4 (Baseline) and 5 (Surgery) is greater than 2 weeks but less than or equal to 4 weeks, the baseline measurements do not have to be re-measured. However, if the window between Visit 4 and 5 is greater than 4 weeks, the baseline measurements must be measured again at next clinic visit (Visit 5 or an unscheduled visit before Visit 5) and recorded on CRF 12: Re-measurement of Baseline Measurements. Additionally, the eligibility of the target tooth should be re-verified at this visit.

If Visit 4 (Baseline) does not occur on the same day of Visit 1 (Screening), the subject eligibility should be verified again at this visit.

Visits 4 (Baseline) and 5 (Surgery) may be performed on the same day.

A summary of all procedures to be performed is listed below.

Summary of Procedures/Measurements:

- Confirm subject eligibility (if this visit is not the same day of Visit 1-Screening)
- Informed Consent for Enrollment must be obtained according to the process described in Section 14.2
- Detailed probing measurements of the potential study teeth sites including:

CONFIDENTIAL

- CAL (calculation)
- PD
- GR
- BOP
- Full set of radiographs or a panorex (if none available within past 6 months) ;
- Full mouth periodontal pocket depth charting except for 3rd molar (if none available from last 6 months);
- Standardized PA radiograph of potential target teeth (if none available within 2 months of Visit 5 - Surgery; see Section 8.1.3 Radiologic Outcomes);
- Confirm eligibility of all target teeth;
- If more than one target tooth is identified, the Investigator will rank the eligible target teeth in order of most severe disease coupled with the most favorable environment. The following criteria, listed in order of importance, will be used to determine the ranking:
 1. Deepest intrabony defect based on radiographic measurement
 2. Smallest vertical angle (smallest coronal width) of defect based on radiographic measurement
 3. Single-rooted
 4. Adjacent teeth have the most healthy periodontal condition (based on amount of bone loss, clinical attachment level and pocket depth)

Thus, eligible target teeth will be ranked numerically starting with “1”.

- Record tobacco use
- Oral hygiene instruction (as necessary)
- Concomitant medication review

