5.0 STUDY DESIGN AND DESCRIPTION

5.1 Study Design

This will be a prospective, randomized, double-blinded, controlled, multi-center, dose-verification clinical study in subjects who require surgical intervention to treat a qualifying periodontal defect. A total of 94 subjects will be randomized to obtain at least 80 evaluable subjects in anticipation of a 15% dropout rate. This study will be conducted in six sites in the United States.

The duration of the study for each subject will be six months following implantation of the study device.

Subjects will participate in a Screening Period lasting up to 2.5 months. Subjects must have been diagnosed to have at least one periodontally related osseous defect to be treated by periodontal reconstructive surgery. Subjects must be systemically healthy and not have any sites suffering from localized juvenile periodontitis. Subjects must not partake in the daily use of smokeless chewing tobacco, pipe or cigar smoking, or smoke more than 10 cigarettes a day or the equivalent.

After a successful screening, eligible subjects will be randomized using variable block sizes for the four treatment groups. The study will be stratified to control for potential differences in healing rates and responses in the treatment based on smoking habits (between non-smokers and moderate smokers).

The treatment groups are:

Treatment I: β -TCP alone (active control)

Treatment II: [REDACTED] GFeBGS: consisting of β -TCP and 0.1% rh-bFGF

Treatment III: [REDACTED] GFeBGS: consisting of β -TCP and 0.3% rh-bFGF

Treatment IV: [REDACTED] GFeBGS: consisting of β -TCP and 0.4% rh-bFGF

Subjects will be evaluated at 2 and 4 weeks and 3 and 6 months following surgery (see Figure 5).

Figure 5 Schematic of Study Visits and Windows

| | Screening period | Pre-treatment procedures | | | Treatment/ Post-treatment follow-up period | | | | |
|-----------|------------------|---------------------------------------|---------------|----------|--|--------------|--------------|--------------|---------------------------------|
| Visit # | Visit 1 | Visit 2 | Visit 3 | Visit 4 | Visit 5 | Visit 6 | Visit 7 | Visit 8 | Visit 9 |
| Procedure | Screening | Pre-treatment | Pre-treatment | Baseline | Surgery | Wk 2 | Wk 4 (1 Mo) | 3 Mo (12 Wk) | 6 Mo/ Early termination (24 Wk) |
| Schedule | <-3 Mo | -2 Mo (\geq 2Wks before Baseline)* | -2 Wks | | | | | | |
| Windows | | (-2 days)* | | Day 1 | \pm 3 days | \pm 3 days | \pm 7 days | \pm 7 days | |

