* Pre-treatment should be performed at least two weeks prior to the Baseline Visit. The study visit window is -2 days; therefore teeth in the target quadrant must undergo all required scaling and planing no more than two months and 2 days prior to surgery.

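### Section 8.3.3 lets Baseline follow a pre-treatment visit held within two weeks of surgery, although three other places require scaling at least two weeks before Baseline

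*Protocol*

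**What the plan says.** Section 8.3.3 governs the Baseline visit (Visit 4). After allowing Screening and Baseline on the same day when no pre-treatment is needed, it permits Baseline after the final pre-treatment visit (Visit 2 or 3) "if the final pre-treatment visit occurs within 2 weeks before surgical treatment". It also states that "Visits 4 (Baseline) and 5 (Surgery) may be performed on the same day".

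Other parts of the protocol set a minimum gap in the opposite direction:

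- **Section 5.1, note to Figure 5:** "Pre-treatment should be performed at least two weeks prior to the Baseline Visit".
- **Section 8.3.1 (Screening):** scaling and planing, where needed, should be done two weeks or more before Visit 4.
- **Section 8.3.2 (Visits 2 and 3):** the same rule is repeated. The listed procedure for these visits is "Perform thorough scaling and planing of all teeth using local anesthetic as necessary", together with oral hygiene instruction.

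Sections 8.3.1 and 8.3.2 add a safeguard. If inflammation caused by pre-treatment is seen at Visit 4, "the Baseline Visit should be postponed until the inflammation subsides".

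**The concern.** The purpose of the two-week gap is to let tissues settle before the reference measurements are taken. The sentence in 8.3.3 allows the gap to be shorter, down to almost nothing.

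Baseline probing matters in several places. Attachment level is calculated from pocket depth and recession (8.1.2). Pocket depth decides the 7 mm inclusion criterion (6.1). The change in attachment level is one of the two parts of the primary composite, with a 1.5 mm threshold (5.2.2). Mean change at three months is compared with a historical 1.5 mm level (5.2.3), and within-group change is tested with paired t-tests (12.1.9).

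If some response to scaling is still to come when Baseline is measured, it is counted as gain after implantation. The historical and within-group comparisons have no concurrent control to remove it. Subjects at the same site could also have baselines taken at quite different intervals after scaling, depending on which section the coordinator followed.

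**Working it through.** The protocol states no figure to reproduce here; this is a check on whether the timing rules are consistent.

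**Inputs.** Put surgery at day 0. Let P be the days from the final pre-treatment visit (with scaling of the target quadrant) to surgery, and B the days from Baseline to surgery.

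- 8.3.3, disputed sentence: P ≤ 14.
- Figure 5 note, 8.3.1 and 8.3.2: P − B ≥ 14.
- 8.3.3, same-day Baseline and surgery allowed, and Baseline cannot follow surgery: B ≥ 0.

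**Step 1: combine the rules.** From P − B ≥ 14 and B ≥ 0, P ≥ 14. Together with P ≤ 14 this gives P = 14, and then B = 0. That is the only solution.

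**Step 2: how much of the permission conflicts.** Take whole-day schedules with P from 1 to 14 and Baseline on a later day than scaling, so B runs from 0 to P − 1. The number of schedules is 1 + 2 + … + 14 = 105, and only P = 14, B = 0 meets the two-week rule. If Baseline may also fall on the scaling day, there are 105 + 14 = 119 schedules. If all three visits may share day 0 as well, there are 120. The single solution is the same each time. These counts show how far the two rules disagree; they do not estimate how many subjects are affected.

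**Step 3: the reverse direction.** Take the outer limit for scaling in the Figure 5 note, two months and two days, as about 62 days (an assumption on month length). Schedules meeting P − B ≥ 14 with P ≤ 62 number 1 + 2 + … + 49 = 1225. Only one of them also has P ≤ 14. Read as a condition instead of a permission, the sentence would exclude practically every compliant schedule.

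**Step 4: examples.** Scaling on day −10 and Baseline on day −3 is allowed by 8.3.3, but the gap is 10 − 3 = 7 days. Scaling on day −28 and Baseline on day −7 has a gap of 28 − 7 = 21 days and is sound under the other three texts, yet it lies outside the 8.3.3 wording.

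**Step 5: the likely source.** The sentences that follow in 8.3.3 deal with the interval from Visit 4 to Visit 5: over two and up to four weeks needs no re-measurement, and over four weeks does. The missing first tier would be Baseline within two weeks of surgery. A pre-treated subject whose Baseline is two to four weeks before surgery must have had pre-treatment more than two weeks before surgery, and 8.3.3 accepts that Baseline. The disputed sentence, taken as a requirement, would clash with its own paragraph. This points to a slip in which the pre-treatment visit was named where Baseline was meant.

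**The case against.** The strongest reply is that this is a drafting slip with little consequence.

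- **The slip is visible from context, and the sentence only permits.** It does not say that the two-week rule is waived, and a site reading the whole protocol meets that rule three times. This makes the intended meaning likely. But the three statements of the rule say only that it should be followed, and 8.3.3 is where a site looks when it books Baseline.
- **The last pre-treatment visit need not involve scaling of the target quadrant.** Section 8.3.1 allows for sustained hygiene instruction and for scaling in other quadrants. For such visits there need be no conflict with 8.3.1 or 8.3.2. However, 8.3.3 makes no such restriction, and the Figure 5 note covers pre-treatment generally.
- **Baseline is postponed if inflammation is seen.** This reduces the risk. It depends on visible signs and fixes no minimum interval.
- **The mechanism is diluted.** At surgery every subject has an open flap, full degranulation and root planing before randomisation (8.3.4), so any remaining response to closed scaling is mixed with the response to open debridement, which counts in every arm's change anyway. This stands, and it is a reason not to claim a particular size of bias.
- **The main comparisons are between arms in a feasibility study not used for labeling.** This also stands. No arm is systematically favoured, and the radiographic half of the composite is not in question.

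**Conclusion.** The contradiction is real and should be corrected. The rule in 8.3.3 and the rule in 5.1, 8.3.1 and 8.3.2 can both be met only with scaling exactly 14 days before surgery and Baseline on the day of surgery. This rests on two assumptions: the final pre-treatment visit includes scaling of the target quadrant, and Baseline does not follow surgery.

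Confidence is high on the textual conflict. The consequence is limited and cannot be quantified from the protocol, which gives neither the size of any residual scaling response nor the number of subjects who would be scheduled this way. The exposed results are mainly the within-group changes, the three-month comparison with the historical 1.5 mm level, and eligibility near 7 mm. Because randomisation follows Baseline, there is no systematic bias between arms. The effect on between-arm differences in composite success, which guide dose selection, cannot be determined.

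**What to change.** Reword the sentence in 8.3.3 so that, for subjects who need scaling, Baseline is held at least two weeks after the last scaling of the target quadrant. If that was the intent, also say that Baseline, not the pre-treatment visit, should fall within two weeks before surgery. The existing provisions for longer Baseline-to-surgery intervals then follow naturally as the next tiers. Keep the postponement for visible inflammation as an addition to the minimum interval.

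The cost is one sentence of protocol text. Sites that had read the sentence literally may need to move some visits; the protocol gives no basis for a number. A sensitivity analysis using the recorded scaling and Baseline dates is optional.
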